5.2.6. Prohibitions and Restrictions

5.2.6.1. Medication

5.2.6.1.1. Stable concomitant medication regimens

Concomitant medication regimens taken for the long-term treatment of pre-existing conditions are allowed if they are in accordance with the inclusion and exclusion criteria, and are stable for at least 4 weeks prior to the first study drug administration and continued without variation of dose or regimen during the study (see Section 5.3.8).

Subjects must remain on a stable medication regimen for pulmonary health (including dose and frequency) for at least 4 weeks prior to the first study drug administration and for the

entire study duration (i.e. until the follow-up visit). Further details are provided in Section 5.3.8.1.

Use of CFTR modulator therapy (e.g. lumacaftor or ivacaftor) is prohibited within 4 weeks prior to the first study drug administration and for the entire study duration.

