6.2. INITIAL SUBJECT AND DISEASE CHARACTERISTICS

Subjects will be asked to come to the clinical study center for the screening visit, which may be scheduled between 28 days and 1 day prior to baseline (Day 1). The CFQ-R will be completed after informed consent was given by the subject, and prior to any other assessments scheduled for that visit. As part of the safety assessments, vital signs will be recorded, a pulse oximetry will be performed to measure oxygen saturation, and a 12-lead ECG will be recorded. Efficacy assessment tests will be performed, including sweat collection and spirometry. Blood and urine samples will be collected for clinical safety laboratory tests, serology, pregnancy test, and FSH test (if applicable). In addition, the following assessments will be done during screening: a complete check of inclusion and exclusion criteria, demographics (recording of year of birth, age and race), a general medical examination including medical and surgical history (including CF-specific medical history e.g. date of diagnosis, sweat chloride concentration prior to any treatment with a CFTR modulator, CFTR mutation, etc.) and questions about smoking habits, alcohol and drug intake, a full physical examination (including height), and weight. Finally, the subject diary will be dispensed.

All AEs (serious and non-serious) and concomitant medications will be reported continuously from the time a signed and dated ICF is obtained until the final follow-up visit.

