6.3.2. Spirometry

Spirometry will be performed to assess pulmonary function at the time points specified in the flow chart. Spirometry must be performed pre-dose at all visits, and additionally between 1 and 2 hours post-dose on Day 1 and Day 29.

The spirometry test must meet the criteria for acceptability and repeatability as defined in the 2005 ATS/ERS guidelines on standardization of lung function testing [7].

If screening spirometry measurements fail to meet acceptability and repeatability criteria in the first 3 efforts, up to 8 repeat spirometry efforts may be performed. If repeat values of the individual assessment(s) satisfy the eligibility criteria and are completed within the screening window, then the subject is eligible for the study.

Clinical study centers will be provided with spiroimeters to be used for all study spirometry assessments. Pulmonary function will be measured in a standardized manner. Spirometry data will be transmitted to a centralized spirometry service for quality review. Subjects should not be informed of their study-related spirometry results during the entire study duration, regardless of whether the subject prematurely discontinues treatment.

At screening, spirometry to determine subject’s eligibility should preferably be performed pre-bronchodilator. If the subject used his/her bronchodilator before the screening visit, screening spirometry is allowed to be performed post-bronchodilator. At all other study visits, spirometry should be performed pre-bronchodilator. If on Day 1, the subject forgets to withhold his/her bronchodilator, all subsequent spirometry testing should be performed post-bronchodilator, to be consistent with the conditions for the baseline measurement. If on Day 1, spirometry is collected pre-bronchodilator, but the subject forgets to withhold his/her

dose of bronchodilator at a subsequent visit, then spirometry should be collected post-bronchodilator for that visit only.

Pre-bronchodilator spirometry is defined as spirometry testing performed for a subject:

- that withheld his/her short-acting β -agonist (e.g. albuterol) or anticholinergic (e.g. ipratropium bromide) for more than 4 hours prior to the spirometry assessment, AND
- that withheld his/her long-acting bronchodilator such as salmeterol or formoterol for at least 12 hours, or longer-acting agents such as indacaterol and tiotropium for at least 24 hours prior to the spirometry assessment.

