4.3. ALGORITHM OF ALLOCATING VISITS TO TIME WINDOWS

All visits (including unscheduled visits but excluding visits without data) will be placed into time windows according to their relative day (DY) in the study, according to the following allocation table:

Visits falling really late in the study will be allocated to a “>Day 29” interval, and will not be shown in tables nor figures, but will only be listed.

Time point label	Target day	Interval lower bound	Interval upper bound
Screening ³	NAP ⁴	NAP ⁴	NAP ⁴
Baseline ¹	NAP ⁴	NAP ⁴	NAP ⁴
Day 1 post-dose ³	NAP ⁴	NAP ⁴	NAP ⁴
Day 15	15	2	21
Day 29	29	22	36
>Day 29 ²	NAP ⁴	37	$+\infty$
Follow-up ³	11-17 days after last visit	NAP ⁴	NAP ⁴

¹ The actual baseline reference value will be determined per parameter as the last available pre-dosing data point, so might differ from this “baseline” visit interval.

² Visits falling really late in the study (relative day > 36; excluding the follow-up visit) will be allocated to a “>Day 29” interval, and will not be shown in tables nor figures, but will only be listed.

³ For the screening, day1 post-dose (vital signs) and follow-up visits, no time window is defined. The visit as recorded in the CRF will be used.

⁴ NAP = Not applicable

For efficacy, PD data, all by-time-point summaries will be based on the visit indicated on the subject’s CRF and will not be placed in time windows.

Tables, figures and listings will present the time points, not the visits.

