4.4. SELECTION OF VISITS

It is possible that more than one visit gets allocated into the same time window. In that case, only one visit will be selected for analysis tables and figures. The nonselected visit(s) will only be listed, and flagged as use=no.

The visit with a relative day (DY) closest to the target day will be selected. If there are multiple visits at the same distance of the scheduled visit day (meaning: equal ABS(DY – target day)), then the one latest in time is selected.

In case of multiple screening visits, the last pre-baseline screening measurement (the last visit happening before the scheduled 'Day 1 predose') is selected for analysis. This value (not the original first screening value) was also used in the clinical center to include the subject in the study.

In case more than one parameter is measured per time point (e.g. for lab), the selection is performed per parameter and per time point, not per “sample” and per time point. Missing values are removed before the selection is made.

As baseline reference point, the last nonmissing pre-dosing value will be used. This is normally the scheduled baseline itself. A missing scheduled baseline value will be imputed with the last nonmissing value of a preceding pre-dosing visit. This can be a screening visit or an unscheduled visit prior to the first dose of study medication. If there is an unscheduled measurement taken after the scheduled baseline, before the first dose of study drug, then this unscheduled measurement will be used instead of the scheduled baseline. If there is an

unscheduled measurement at the same datetime as the scheduled baseline, then it is assumed that the unscheduled measurement is taken after the scheduled baseline.

In case the screening visit is used to impute the baseline, the original screening visit as well as the imputed baseline will be presented in the tables. In the listings, only original screening data will be shown: the original screening visit will be shown and flagged as “reference” visit. The imputed baseline will not be shown.

In case an unscheduled visit is used to impute the baseline, the visit will be renamed to “baseline”. The imputed baseline will be presented in the tables. In the listings, the original unscheduled data will be shown and flagged as “reference” visit.

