9.2. SPIROMETRY

9.2.1. Parameters

During study visits on Days 1, 15 and 29, spirometry must be performed before the morning dose. On Day 1 and Day 29, the spirometry test is to be performed prior to the morning dose of study drug and an additional spirometry must be performed after the study drug intake around 1-2 hours post-dose.

Spirometry can be performed pre-bronchodilator* or post-bronchodilator at screening but should take place prior to bronchodilator use at all other visits. But in practice, if on Day 1, the subject forgets to withhold his/her dose of bronchodilator then all subsequent spirometry should be collected post-bronchodilator, to be consistent with the conditions for the baseline measurement. And if on Day 1 spirometry is collected pre-bronchodilator, but then at a subsequent visit the subject forgets to withhold his/her dose of bronchodilator, then spirometry should be collected post-bronchodilator for that visit only.

* pre-bronchodilator is defined as:

- short-acting more than 4 hours prior to the spirometry assessment
- long-acting bronchodilator at least 12 hours or 24 hours prior to the spirometry assessment

(a spirometry assessment with no use of bronchodilator is equivalent to a pre-bronchodilator assessment)

The values will be used as available via the data transfer from the central laboratory (████████).

Note that at all post-baseline (Day 1) visits:

- Spirometry data taken inconsistently with the baseline will be excluded from the analysis (i.e. if spirometry was performed post-bronchodilator and the one at baseline was performed pre-bronchodilator or if spirometry was performed pre-bronchodilator and the one at baseline was performed post-bronchodilator).
- Spirometry that should be assessed pre-dose and was done post-dose will be excluded from the analysis.
- Spirometry, 1-2h post-dose assessment that was done pre-dose will be excluded from the analysis.

Data with a quality grade of D, E or F will be excluded too.

Quality*	Criteria
A	At least 3 acceptable efforts AND the difference between the best two FEV ₁ and FVC values is equal to or less than 100 ml (80 ml if FVC < 1.0 L)
B	At least 3 acceptable efforts AND the difference between the best two FEV ₁ and FVC values is equal to or less than 150 ml (100 ml if FVC < 1.0 L)
C	At least 2 acceptable efforts AND the difference between the best two FEV ₁ and FVC values is equal to or less than 200 ml (150 ml if FVC < 1.0 L)

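### SAP 4.4 lets a screening value replace a missing Day 1 efficacy baseline without requiring Day 1 test conditions; for spirometry this can produce a false change of zero

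*SAP*

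**What the plan says.** **Baseline.** SAP 4.4 takes the last nonmissing pre-dose value as the reference. Where Day 1 is missing, "A missing scheduled baseline value will be imputed with the last nonmissing value of a preceding pre-dosing visit", and "This can be a screening visit or an unscheduled visit prior to the first dose of study medication". A footnote in SAP 4.3 agrees: "The actual baseline reference value will be determined per parameter as the last available pre-dosing data point". Neither section conditions this on bronchodilator state or modulator washout, and neither exempts the efficacy parameters.

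**Spirometry.** Protocol 6.3.2 prefers pre-bronchodilator testing at screening but adds: "If the subject used his/her bronchodilator before the screening visit, screening spirometry is allowed to be performed post-bronchodilator". For the rest of the study, "At all other study visits, spirometry should be performed pre-bronchodilator". SAP 9.2.1 then provides: "Spirometry data taken inconsistently with the baseline will be excluded from the analysis". It spells out both mismatches, including a pre-bronchodilator test set against a post-bronchodilator baseline.

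**Missing data.** SAP 5.4.2 carries the last nonmissing efficacy result forward, and the baseline may be that result. LOCF is the primary imputation (SAP 7.1.3).

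**Modulators.** Under Protocol 5.2.6.1.1, CFTR modulator therapy "is prohibited within 4 weeks prior to the first study drug administration and for the entire study duration". Screening may take place from 28 days to 1 day before Day 1 (Protocol 6.2).

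**The concern.** All three efficacy endpoints are changes from baseline, so a baseline taken in a different state puts an error into every change computed from it. For spirometry, two rules that are sensible on their own combine badly. A screening test in the permitted but non-preferred state becomes the reference, and the consistency rule then discards the tests that were done as the protocol asks.

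The modulator question is milder. A screening value from a subject whose washout is incomplete may still carry some effect of the earlier drug. As a baseline it would make sweat chloride look too low, so that the fading of the old drug appears as a rise during the study. That would hide benefit in a GLPG2222 group and create apparent worsening on placebo.

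**Working it through.** The plan gives no figure for this rule, so there is none to reproduce. The check traces the rules and then puts a scale on the result.

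**1. Spirometry, Day 1 value missing, screening post-bronchodilator**

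- SAP 4.4: the post-bronchodilator screening value becomes baseline.
- Protocol 6.3.2: Day 15 and Day 29 tests are done pre-bronchodilator. The protocol's provision for matching later tests to Day 1 depends on a Day 1 test having been done, so it does not help here.
- *Reading A: baseline in SAP 9.2.1 is the SAP 4.4 reference value.* The Day 15 and Day 29 tests do not match and are excluded. SAP 5.4.2 fills the pre-dose time points with the baseline, so change = baseline − baseline = 0. A post-dose time point with no earlier valid post-dose test is also filled with the baseline. The observed-case change is missing.
- *Reading B: baseline in SAP 9.2.1 is the Day 1 test only.* Nothing is excluded, and the change is a pre-bronchodilator value minus a post-bronchodilator value. If the bronchodilator raises FEV₁, the change is biased downward.

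Under A the subject's data are replaced by a constant; under B unlike states are subtracted.

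**2. Scale for spirometry under Reading A**

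Allocation of 2:2:1 in 25 subjects gives 10 per dose group, and pooled placebo is 5 + 5 = 10. If k of n subjects have their change set to 0, the group's mean change shrinks by about k/n: 1/10 = 10% for one subject, 2/10 = 20% for two.

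**3. Modulator washout**

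A compliant subject has taken no modulator for at least 28 days at first dose. If screened d days before Day 1, the subject has been off modulator at screening for at least 28 − d days:

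| Screening day | Minimum days off modulator |
|---|---|
| −28 | 0 |
| −14 | 14 |
| −7 | 21 |

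Incomplete washout at screening is therefore possible. Being essentially still on drug is the limiting case only.

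**4. Scale for sweat chloride**

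The documents give no residual effect. Assume a shift s of 5 to 15 mmol/L in one subject of 10. The error in the group's mean change is s × k/n:

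- 5 × 1/10 = 0.5 mmol/L
- 15 × 1/10 = 1.5 mmol/L

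With the planned SD of 10 mmol/L (Protocol 7.1), the standard error of a difference between two groups of 10 is 10 × √(2/10) = 4.5 mmol/L. The shift is 0.5/4.5 = 0.1 to 1.5/4.5 = 0.3 of that.

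**5. Does ANCOVA remove it?**

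A simulation used five groups of 10, SD of change 10, an assumed baseline SD of 8 or 12, and a true difference of −14. One subject in the active group had a baseline lowered by s. The mean estimate was about −13.5 for s = 5 and −13.0 for s = 10, so adjustment left nearly all of the error. The simulation took change to be unrelated to baseline. If follow-up values regress toward the mean, ANCOVA would absorb part of the shift.

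**The case against.** **Two events must coincide.** Day 1 must be missing and the screening value must be unsuitable, and the documents give a rate for neither. Sweat is collected from both arms, sites are encouraged to choose subjects who produce enough, and the main parameter uses the arm with the greater volume. The 25 mmol/L discard touches only the sensitivity parameter. Post-bronchodilator screening is the exception. All of this stands, and it limits the number affected. Routes to a missing value remain: too little sweat, a test not done, or a grade D to F test if that exclusion applies to Day 1.

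**The exclusion may not reach an imputed baseline.** SAP 9.2.1 ties baseline to Day 1 in places, and its change formula refers to Day 1 pre-dose. A reader might infer that the loss of on-treatment tests is settled; it is not, because the text supports two readings. The ambiguity does not rescue the rule, since Reading B also gives a wrong change.

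**Prior modulator users.** A reader might infer that anyone who stops a modulator for the study is screened while on it. The 28 − d calculation shows otherwise, and neither the residual effect nor the share of such subjects is given. This limb holds only as possible partial washout.

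**Small, exploratory and visible.** The sweat chloride shift is a fraction of a standard error, and the study calls itself exploratory. Tables show both the screening value and the imputed baseline, and listings flag the reference visit. That makes the substitution traceable but does not correct the estimate. No planned sensitivity analysis omits imputed baselines.

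**Conclusion.** The point holds. SAP 4.4 allows an efficacy baseline taken under conditions that the protocol does not accept on Day 1. For spirometry the stated rules give a wrong change from baseline on either reading of SAP 9.2.1. Under the literal reading, one affected subject costs about 10% of a 10-subject group's mean change.

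The modulator part is secondary. It rests on an assumed shift of 5 to 15 mmol/L and gives 0.5 to 1.5 mmol/L in a group mean, about 0.1 to 0.3 of the standard error of a difference. Both parts apply only when the Day 1 value is missing, which is probably uncommon.

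This is worth correcting because it is cheap and settles the baseline before results are seen. It does not by itself threaten the study's conclusions. A reader might also infer that correcting the rule recovers the subject's tests for the endpoint. It does not: without a valid baseline there is no change from baseline, so the gain is a missing value in place of a false one.

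**What to change.** - **SAP 4.4.** For efficacy parameters, let a screening or unscheduled pre-dose value replace a missing Day 1 value only if it meets the protocol's own Day 1 conditions: pre-bronchodilator for spirometry, and the protocol's 4-week modulator-free interval already complete for sweat chloride, spirometry and CFQ-R. Otherwise leave that parameter's baseline missing and keep the on-treatment tests in the summaries of actual values.
- **SAP 9.2.1.** State how the consistency exclusion applies when baseline is imputed or missing, including for a subject whose Day 1 test was attempted post-bronchodilator but is not usable. Reconcile the references to Day 1 pre-dose with SAP 4.4.

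The condition should not be defined by the state of the on-treatment tests. That would let post-randomization data decide whether a baseline exists, and it is undefined when a subject's later tests are in mixed states, which Protocol 6.3.2 allows.

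The cost is a few sentences. Bronchodilator state is already needed for SAP 9.2.1, and therapy dates are already used in SAP 8.7.1. The downside is an occasional subject with no change-from-baseline value for one parameter.

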4.5. HANDLING OF UNSCHEDULED ASSESSMENTS

If there is an unscheduled measurement at the same datetime as a scheduled visit, then it is assumed that the unscheduled measurement is taken after the scheduled visit.

Unscheduled measurements prior to use of the study drug: see section 4.4.

Unscheduled measurements after the first dose of study drug: place into time window (section 4.3) and selection will be made according rules defined in section 4.4.

5. HANDLING OF DATA

5.1. CALCULATION OF DESCRIPTIVE STATISTICS

For continuous parameters, descriptive statistics will be presented when $N \geq 2$ unless otherwise specified. When $N=1$, the observation will not be shown in the table but only in the listing.

Descriptive statistics will include at least the following:

- the number of nonmissing data points (N)
- the arithmetic mean
- the standard error (SE)
- the median, minimum and maximum
- 95% confidence interval of the mean (only when requested).

For PK plasma concentrations, descriptive statistics will include:

- the number of nonmissing data points (N)
- the number of data points above the lower limit of quantification (LLOQ)
- the arithmetic mean
- the standard error (SE) and standard deviation (SD)
- the median, minimum, and maximum
- the coefficient of variation (CV%)
= $100 \times (\text{standard deviation} / \text{arithmetic mean})$
- the geometric mean = $\exp(\text{arithmetic mean of ln-transformed data})$
- the geometric coefficient of variation (CV%)
= $100 \times \sqrt{e^{(\text{standard deviation of ln-transformed data})^2} - 1}$

Note that at least 50% of the subjects must have a plasma level above the lower limit of quantification before these descriptive statistics are calculated. If less than 50% of values were quantifiable, only the arithmetic mean (with minimum and maximum) will be presented with the original calculated value, the other descriptive statistics will be listed as “NC” (not calculated). If the calculated mean is below the lower limit of quantification, then it will be presented as below the limit of quantitation (BLOQ). The minimum will be “BLOQ”, and the maximum will be derived from the actual data. Standard deviation (SD) and CV% will be reported as “NC”. The plasma concentrations of GLPG2222 will be presented with 3 significant digits in the original concentration unit (i.e.: 8.356 and 1839 ng/mL will be rounded to 8.36 and 1840 ng/mL, respectively). The descriptive statistics should be rounded to the same number of significant digits as the individual values.

For derived PK parameters, descriptive statistics will include:

- the number of nonmissing data points (N)
- the arithmetic mean
- the standard error (SE) and/or standard deviation (SD)
- the median, minimum, and maximum
- the coefficient of variation (CV%)
- the geometric mean
- the geometric coefficient of variation (CV%).

Note that at least 50% of the subjects must have a nonmissing result before these descriptive statistics are calculated. If less than 50% of values were available, only the arithmetic mean will be presented with the original calculated value, the other descriptive statistics will be listed as “NC” (not calculated). Pharmacokinetic parameters will be presented with 3 significant digits (i.e.: 8.356 and 1839 ng/mL will be rounded to 8.36 and 1840 ng/mL, respectively) except for t_{max} , which will be presented with 1 decimal. The descriptive statistics should be rounded to the same number of significant digits as the individual values.

5.2. CALCULATION OF PERCENTAGES

Missing values will not be included in the denominator count when computing percentages.

